**Table 2. Social Risk Factors**

	Definition	Sources
All observable risk factors	See Table 1	See Table 1
Recent arrest	Reported being arrested in the year prior to the survey date	Darling et al., 2024
High stress	Scored 9 or higher on PSS4	Darling et al., 2024 (mental health challenges); Stamuli et al., 2015 (mental illness). 9+ for moderate or severe perceived stress cutoff obtained from Eick et al., 2022
Depression	Scored 3 or higher on PHQ2	Darling et al., 2024 (mental health challenges); Kristensen et al., 2017 (uses the Edinburgh Postnatal Depression Scale (EPDS)); Stamuli et al., 2015 (mental illness)
Housing insecurity	Moved 2+ times in the previous year or if they reported not living in a private residence (dorm room, homeless shelter)	Darling et al., 2024; Catherine et al., 2020
Substance use	Reported either: 1) any smoking in the 3 months before or during	Darling et al., 2024; Stamuli et al., 2015

	pregnancy, or 2) more than 7 drinks per week on average in the 3 months before pregnancy	
Low social support	Responded "yes" to the following social support questions 0-2 times: "Someone to loan \$50", "Someone to help you if you were sick and needed to be in bed", "Someone to drive you to clinic or doctor if you needed a ride", "Someone to talk with about your problems"	Darling et al., 2024; Stamuli et al., 2015 (isolated)
Not fluent in English	Reported not speaking English very well or not at all	Darling et al., 2024 (migrant)
Limited access to healthcare	Reported not having a place for general healthcare if sick or needs advice about health, AND reported obtaining care at a hospital ER in the 6 months prior to the survey	Darling et al., 2024 (health human resource issues; lack of providers); Cavallaro et al., 2022 (unplanned hospital admission 2y prior to 20w gestation)
Do not have a driver's license	Does not have their own driver's license	Rice et al., 2024; Bellerose et al., 2022
Low financial independence	Respondent reported having neither their own bank account nor access to their own credit card	Stevens et al., 2024
Fair/poor health	Health self-reported as fair or poor before pregnancy	Price et al., 2017
Limited relationship with child's father	Does not see or talk to the father of the child daily	Darling et al., 2024 (unmarried); Tereno et al., 2022 (declares intention to raise child without the father); Foulon et al., 2015 (being a single parent or unmarried); Stamuli et al., 2015 (not married)

**Table 3. Prevalence of vulnerabilities in sample of mothers with an index birth**

	Nurse Home Visiting Group	Usual Care Group
Living in high poverty area	1029/3292 (31.3%)	509/1636 (31.1%)
Recent arrest	152/3269 (4.6%)	73/1626 (4.5%)
High stress	478/3250 (14.7%)	235/1615 (14.6%)
Depression	630/3270 (19.3%)	305/1631 (18.7%)
Housing insecurity	567/3295 (17.2%)	298/1637 (18.2%)
Have not completed high school	742/3295 (22.5%)	354/1637 (21.6%)
Substance use	823/3295 (25%)	441/1637 (26.9%)
Low social support	364/3295 (11%)	181/1637 (11.1%)
Under 18	225/3295 (6.8%)	117/1637 (7.1%)
Not fluent in English	100/3295 (3%)	50/1637 (3.1%)
Food insecurity	811/3286 (24.7%)	375/1630 (23%)
Limited access to healthcare	598/3279 (18.2%)	285/1625 (17.5%)
Do not have a driver's license	940/3252 (28.9%)	467/1611 (29%)
Low financial independence	961/3295 (29.2%)	477/1637 (29.1%)
Fair/poor health	419/3295 (12.7%)	180/1637 (11%)
Limited relationship with child's father	662/3281 (20.2%)	320/1630 (19.6%)
3+ vulnerabilities	1746/3295 (53%)	836/1637 (51.1%)
5+ vulnerabilities	752/3295 (22.8%)	390/1637 (23.8%)
10+ vulnerabilities	23/3295 (0.7%)	15/1637 (0.9%)
Number of vulnerabilities	Nurse Home Visiting Group	Usual Care Group
Mean (SD)	3.02 (2.19)	2.99 (2.23)
Median (IQR)	3 (1, 4)	3 (1, 4)

**Table 4. Prenatal outcomes**

	Primary/secondary	Desired direction (increase or decrease)
At least adequate prenatal care	secondary	increase
Anatomy scan ultrasound (18-22w)	secondary	increase
Dental visit during pregnancy	secondary	increase
Recommended gestational weight gain	exploratory	increase
Number of prenatal visits	exploratory	increase
Number of prenatal ultrasounds	exploratory	increase
Gestational diabetes test (24-28w)	secondary	increase
Tdap vaccination (27-36w)	exploratory	increase
Group B streptococcus test (35-37w)	secondary	increase
Maternal fetal medicine visit	exploratory	increase

Note: Tables 4-10 include all primary, secondary and exploratory outcomes from the published papers resulting from this study, except those where the desired direction of the effect of NFP cannot be determined.

**Table 5. Birth outcomes**

	Primary/secondary	Desired direction (increase or decrease)
Composite adverse birth outcome	primary	decrease
Large for gestational age	secondary	decrease
NICU admission of at least overnight	secondary	decrease
Severe acute maternal morbidity	secondary	decrease
Small for gestational age	secondary, in primary	decrease
Low birth weight (<2500g)	secondary, in primary	decrease
Very low birth weight (<1500g)	secondary, in primary	decrease
Preterm birth (<37w gestation)	secondary, in primary	decrease
Extremely preterm (<28w gestation)	secondary, in primary	decrease
Perinatal mortality	secondary, in primary	decrease
Neonatal morbidity	secondary, in primary	decrease
Gestational age at birth in weeks	secondary	increase

**Table 6. Contraception and birth spacing outcomes**

	Primary/secondary	Desired direction (increase or decrease)
Inter-birth interval of <21m	primary	decrease
Inter-birth interval of <15m	secondary	decrease
Inter-birth interval of <24m	secondary	decrease
Time to first FP counseling or service (months from pregnancy)	secondary	decrease
Any FP counseling or service (12w, 1y)	secondary	increase

**Table 7. Postpartum outcomes**

	Primary/secondary	Desired direction (increase or decrease)
Maternal mortality (1y)	secondary	decrease
Postpartum visit (12w)	secondary	increase
Hospitalization (12w/1y)	exploratory	decrease
Outpatient visit (12w/1y)	exploratory	increase

**Table 8. Mental health outcomes**

	Primary/secondary	Desired direction (increase or decrease)

Any outpatient treatment or diagnosis (preg-60d)	secondary	increase
Antidepressant prescription (preg-60d)	secondary	increase
Outpatient mental health visit (preg-60d)	secondary	increase
Treatment follow up (within 120d)	secondary	increase
Mental health related emergency/inpatient visit (preg-1y)	secondary	decrease
Number of mental health related emergency/inpatient visits (preg-1y)	secondary	decrease
Neonatal abstinence disorder or maternal drug/substance use (2y)	secondary	decrease
Maternal experience of violence or homicide (2y)	secondary	decrease

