#### Maternal utilization of mental health services

Analyses of outcomes related to maternal utilization of mental health services is also planned as a stand-alone analysis. NFP guidelines require nurses to screen for depression and anxiety at pre-specified intervals throughout the program, and to follow their agencies' protocols for referral and care coordination for women who screen positive. While directly measuring the

prevalence of depression and anxiety in our study sample would help us assess the impact of NFP on mental health, our study design relies exclusively on administrative data sources for outcome measurement. Therefore, our study design will seek to analyze how NFP changed the utilization of mental health services during the perinatal period.

We include all women with an index birth in our analytic sample, regardless of whether they had a prior mental health diagnosis before pregnancy. Because few women in our study are enrolled in Medicaid prior to pregnancy, we cannot observe prior diagnoses or identify treatment initiation. However, we expect rates of prior mental health diagnoses before pregnancy to be equal across treatment and control arms. Because the outpatient mental health treatment outcomes rely exclusively on Medicaid claims, we will restrict the analytic sample for outpatient outcomes to those women who retain full Medicaid coverage through 60 days postpartum. We will not restrict the sample for inpatient mental health outcomes as these rely on utilization that will be observable in all-payer hospital discharge data, regardless of payer.

While the medical definitions for depression and anxiety are distinct, we examine them together because they are comorbid conditions and NFP screens for them simultaneously. We define outpatient mental health treatment as a composite outcome of either a diagnosis for depression/anxiety/stress reaction or a filled prescription for antidepressants/anxiolytics or an outpatient psychotherapy visit during pregnancy or the first 60 days postpartum. We list the ICD-10 diagnosis codes, therapeutic class codes, and Current Procedure Terminology (CPT) codes used to define these outcomes in Tables 1.4, 1.5, and 1.6. Consistent with prior research, we consider all outpatient psychotherapy visits, including individual, family or group therapy to be mental health visits.

Table 1.4. Diagnosis codes for depression/anxiety/stress reaction

Code description	ICD-10 Code(s)

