In our clinical trials registry, we defined a measure of mental health treatment follow-up care as: a second antidepressant prescription or outpatient mental health visit within 120 days of the initial treatment ("acute phase"). However, as noted above, differential Medicaid coverage rates between the treatment arms after 60 days postpartum may preclude us from measuring the treatment effect for this outcome reliably. For example, if treatment group members are more likely to be enrolled in Medicaid after 60 days postpartum than control group members, observed differences in mental health treatment patterns between the treatment and control groups could be due to group differences in the composition of who remains on Medicaid.

To assess whether attrition from full-coverage Medicaid plans affects the comparability of the treatment and control groups, we will assess overall attrition and differences in attrition between the treatment and control groups at the following time points: 60 days (for our main outpatient mental health treatment outcomes), 6 months, 12 months and 24 months postpartum (for other potential measurement periods of interest). We do not consider enrollment in partial-coverage Medicaid plans (such as Family Planning) since these plans cover mental health screenings, but do not reimburse for medications or psychotherapy. Specifically, we will compare partial and continuous enrollment rates in full coverage plans between treatment and control groups at each time point. Continuous coverage will be measured using Medicaid enrollment data and will be defined as enrollment during all months, starting with the month of childbirth through 60 days, 6 months, 12 months and 24 months postpartum. It's possible that while average Medicaid enrollment will not differ between the two groups, the type of women retaining coverage could be affected by NFP. Therefore, we will also test whether the treatment and control group members who remain in the analytic sample at each time point are similar on important baseline characteristics using a joint F-test.

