#### **Outcomes**

Our analysis will focus on pre-registered primary outcomes and indices of secondary outcomes derived from 8 manuscripts that are either published or forthcoming reporting on trial results (birth outcomes, prenatal outcomes, family planning outcomes, postpartum outcomes, mental health outcomes, social service outcomes and child outcomes). These indices will be created using the method developed by Kling, Liebman and Katz (2017). More sophisticated indexing techniques, such as the Optimus index developed by Anderson and Magruder (2023) will also be explored. These outcomes are specified in Table 4-10 with indications of whether participating in NFP would be expected to increase or decrease the outcome. For outcomes related to the use of the emergency department, participation in NFP might be expected to either increase the outcome (i.e. by identifying health challenges that need immediate attention) or decrease the outcome (i.e. by offering a trusted source of information that can reduce unnecessary care-seeking). We include an additional index of ED related outcomes in Table 11.

We will also consider exploratory analyses within the treatment group to determine whether characteristics that predict program outcomes overlap with those that predict program

participation. In this analysis the outcomes will be the number of home visits completed and the duration of participation in the program.

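### Addendum 4 lists the 120-day mental health follow-up outcome for its index without the Medicaid coverage condition that Addendum 1 attaches to outpatient measurement after day 60 postpartum

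*SAP*

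**What the plan says.** Addendum 4, under Outcomes, sets the scope: "Our analysis will focus on pre-registered primary outcomes and indices of secondary outcomes derived from 8 manuscripts". Mental health is one of the areas named. The content of the indices is then tied to the tables: "These outcomes are specified in Table 4-10 with indications of whether participating in NFP would be expected to increase or decrease the outcome". The note under Table 4 gives the only ground for leaving an outcome out: "except those where the desired direction of the effect of NFP cannot be determined". Table 8 lists "Treatment follow up (within 120d" as a secondary outcome with desired direction increase. The other three outpatient rows of Table 8 are labelled as running from pregnancy to 60 days; this row is not.

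Addendum 1, under Maternal utilization of mental health services, gives the registered definition: "a second antidepressant prescription or outpatient mental health visit within 120 days of the initial treatment". It then warns that "differential Medicaid coverage rates between the treatment arms after 60 days postpartum may preclude us from measuring the treatment effect for this outcome reliably". For outpatient outcomes, which rest on Medicaid claims alone, the plan is to "restrict the analytic sample for outpatient outcomes to those women who retain full Medicaid coverage through 60 days postpartum". Addendum 1 holds most outpatient outcomes to that period. It will consider 6, 12 and 24 months postpartum only if the two arms are equally likely to be in full-coverage plans. It plans by-arm comparisons of full-coverage enrolment at 60 days and at 6, 12 and 24 months, with a joint F-test on baseline characteristics of the women who remain.

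Addendum 1 is dated 20 January 2021 and Addendum 4 is dated 5 February 2025. Addendum 4 states that its analyses had not been performed when it was submitted.

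**The concern.** Followed as written, Addendum 4 places in an index a component that the SAP itself says may not give a reliable treatment effect, without the safeguard the SAP set for measurement after day 60.

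Loss of full coverage after day 60 is a real prospect here. SAP Table 2 gives income limits of 199% of the poverty line for pregnant women against 67% for parents in each January from 2016 to 2020. Section 3.5 of Addendum 3 says that NFP may affect whether Medicaid is kept past 60 days. Addendum 1 notes that partial plans such as Family Planning pay for neither medication nor psychotherapy, so a woman who moves to one disappears from the claims that define this outcome.

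If NFP changes how many women, or which women, keep full coverage, recorded follow-up can differ between arms with no difference in care. The index would count that as benefit. The forest could read it as a difference in benefit between groups if coverage loss also varies with baseline characteristics.

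**Working it through.** The SAP gives no figure for this outcome to reproduce. The check is how far the 120-day window can run past the coverage that the sample guarantees.

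**Inputs**
- Window: 120 days from initial treatment (Addendum 1).
- Treatment counted: pregnancy to 60 days postpartum (Addendum 1).
- Coverage guaranteed by the sample rule: to day 60 postpartum (Addendum 1).
- Latest gestation at enrolment: 27 weeks 6 days, or day 195 (Protocol 4.4). It is used only as one end of the range, since Addendum 1 counts treatment from pregnancy, not from enrolment.
- Assumed: a 280-day pregnancy and evenly spread first-treatment dates. The documents give no distribution of dates.

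**By day of first treatment.** Let t be the day of first treatment relative to birth. The window ends on day t + 120. The share of it after day 60 is (t + 60)/120, limited to between 0 and 1.

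| First treatment | Window ends (day after birth) | Share after day 60 |
|---|---|---|
| 90 days before birth | 30 | 0% |
| 60 days before birth | 60 | 0% |
| 30 days before birth | 90 | 25% |
| day of birth | 120 | 50% |
| 30 days postpartum | 150 | 75% |
| 60 days postpartum | 180 | 100% |

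**Averages.** Suppose starts are spread evenly from gestation day s to 60 days postpartum, a span of 280 − s + 60 = 340 − s days. Crossing starts occupy the last 120 days of that span, so the proportion with any part of the window past day 60 is 120/(340 − s). Among those, the share past day 60 rises evenly from 0 to 1 and averages one half. The overall mean share is therefore 60/(340 − s).

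| Starts from | s | Any crossing | Mean share past day 60 |
|---|---|---|---|
| start of pregnancy | 0 | 120/340 = 35% | 60/340 = 18% |
| 12 weeks | 84 | 120/256 = 47% | 60/256 = 23% |
| 18 weeks | 126 | 120/214 = 56% | 60/214 = 28% |
| 27 weeks 6 days | 195 | 120/145 = 83% | 60/145 = 41% |

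For postpartum starts only, every window crosses, and the mean share is (50% + 100%)/2 = 75%.

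**Reach of the planned checks.** The latest window ends on day 60 + 120 = 180 postpartum, close to the planned 6-month comparison. That comparison counts from birth, however, and covers the whole sample. It does not show whether treated women were covered through their own day 120.

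**The case against.** The strongest reply is that nothing has been repealed. Addendum 1 still pre-specifies the attrition comparisons and the F-test. Addendum 4 came four years later and draws on manuscripts that were published or forthcoming. The check may have been done and passed, and the final sample for this outcome may be defined in a paper not reproduced here. This stands as far as it goes: a reader might infer that the check was skipped, and the documents do not show that. They also do not show that it was met, and Addendum 4 does not make the row depend on it.

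Second, a reader might infer that most of the window lies after day 60, or that the outcome cannot be measured. Neither follows. The window counts from treatment, not birth. In every even-timing case that includes pregnancy starts, the mean share past day 60 stays below one half, and a second claim made before coverage ends is still captured. Addendum 1 says that differential coverage may prevent reliable measurement; it does not say that any loss of coverage makes the outcome unmeasurable. It also says treatment initiation cannot be identified, so women already in treatment may first appear early in pregnancy. That would lower the crossing share.

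Third, it is tempting to say that a woman who loses coverage is scored as having no follow-up, so that better retention or earlier treatment raises the rate. The SAP does not give the scoring rule. Its discussion concerns who remains on Medicaid, which fits attrition at least as well. The problem survives either rule: scoring as absent lowers recorded follow-up where coverage is lost, and dropping women conditions on something NFP may change.

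Fourth, this is one of eight rows in one index, and a bias that is the same for all women would not by itself create apparent heterogeneity. That limits the weight of the point. It does not remove it, because the index effect itself would still be shifted.

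**Conclusion.** The point holds as an unmet condition within the SAP. Addendum 4 admits the 120-day outcome to the mental health index set with undeterminable direction as the only ground for exclusion. Addendum 1 flags the same outcome as possibly not reliably estimable and ties longer outpatient periods to equal full coverage.

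The exposure is partial. It is nil for treatment first recorded 60 or more days before birth and largest for postpartum starts. The crossing and mean-share ranges above rest on assumed even timing and a 280-day pregnancy. They measure how much of the window is at risk, not the size of any bias. That size depends on by-arm coverage and on the scoring rule, and the documents give neither. The change should be made before the analysis is run, but the point does not threaten the trial's primary outcomes.

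**What to change.** Amend Addendum 4 as follows.

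1. Compute the main Table 8 index without this row, unless the Addendum 1 checks (equal full-coverage enrolment by arm, and the joint F-test) show balance when extended to each woman's 120-day window. State in advance what counts as balance, since Addendum 1 gives no threshold.
2. Report index and forest results with and without the row, together with by-arm full coverage through day 120 after initial treatment.
3. State how women who lose full coverage within the window are scored.

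One alternative should not be adopted: recoding the outcome to count only first treatment at least 60 days before delivery with a second contact within 120 days, and zero otherwise. It keeps the window inside covered time but mixes when treatment starts with whether it is followed up. Addendum 1 expects NFP may bring treatment forward; that alone would raise the indicator, and later starters with genuine follow-up would count as failures.

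The cost is SAP wording, one coverage table and a second run of the index and forest. The downside is small: a registered secondary outcome may appear only in the sensitivity version of the index.

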**Table 10. Social services outcomes**

	Primary/secondary	Desired direction (increase or decrease)
SNAP or WIC (preg)	secondary	increase
Number months on SNAP or TANF (2y)	secondary	increase
SNAP or TANF churn (2y)	secondary	decrease

SNAP receipt (0-12m, 12-24m)	exploratory	increase
TANF receipt (preg-2y)	exploratory	increase
WIC receipt (preg)	exploratory	increase

**Table 11. Emergency Department (ED) use (descriptive)**

Outcome	Period	Primary/secondary	Desired direction
Number of ED visits (mother)	Prenatal	secondary	N/A
Visit to ED (child)	2 years	secondary	N/A
Number of visits to ED (child)	2 years	secondary	N/A
ED without admission (child)	0-12 months, 12-24 months	exploratory	N/A
Emergent ED visit (mother)	12 weeks, 1 year	exploratory	N/A
ED without admission (mother)	12 weeks, 1 year	exploratory	N/A
Nonemergent ED visit (mother)	12 weeks, 1 year	exploratory	decrease

